#### **Analysis of AF burden in patients crossed over from sham control to experimental group**

At the end of week three, patients in the sham control group will be given the option to receive the active treatment and treated the same way as patients on the treatment arm for weeks 1-3. Patient characteristics will be summarized for the subset of patients who accept this option to cross over to active treatment. The averages and SDs of AF burden will be computed for each week from baseline to week 6 for this group, and displayed graphically. Linear mixed models may be employed to explore the temporal changes in this subset of patients.

---

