## 1 PROTOCOL SUMMARY

### 1.1 SYNOPSIS

**Title:** Using Electrical Nerve Stimulation to Control Atrial Fibrillation

**Study Description:** Patients will have a 1:1 randomization to receive subcutaneous electrical nerve stimulation (ScNS) to observe if the stimulation can reduce atrial fibrillation burden in patients with symptomatic atrial fibrillation (AF). All subjects will undergo the implant of a neurostimulator lead. The experimental group will receive stimulation and the control group will not receive stimulation. All subjects will complete the same follow up visits to compare the 2 groups. The control group will have an option to cross over to the experimental group 3 weeks post-randomization to receive the stimulation. They will repeat the baseline visit, procedure visit and all follow-up visits post-procedure.

**Objectives:** **Primary Objective:** To test the hypothesis that chronic subcutaneous nerve stimulation can reduce AF burden in patients with severe symptomatic AF unresponsive to conventional therapies

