## 1.2 SCHEMA

\* Eligibility monitoring with mobile cardiac telemetry provided by Preventice will only serve as an option for potential patients that do not have any clinical ePatch monitoring completed in the past 6 months. Potential patients that have ePatch monitoring results with no change in medication since then, do not have to undergo mobile cardiac telemetry during Eligibility visit. \*\* Activities are to be repeated for control subjects only who choose to crossover to experimental group prior the second procedure. \*\*\*Second procedure is to be done within two weeks of the Week 3 Visit for crossover patients, if not, patient must complete another pre-op visit two weeks before the procedure. Pre-op visit will entail Labs (CBC, BMP), INR if patient is taking Coumadin, 12 Lead EKG and pre-op instructions.

All patients will have baseline cardiac rhythm monitoring using standard ECG patch electrodes. Cardiac rhythm monitoring will be done with clinically available 7-day non-invasive Mobile Cardiac Telemetry.

Among them, the 7-day non-invasive Mobile Cardiac Telemetry provided by Preventice will be performed during the two weeks of ScNS to ensure patient safety. The Bittium Faros monitor, a non-invasive patch electrode, will be applied at similar time points as Preventice Mobile Cardiac Telemetry device to monitor skin sympathetic nerve activity. Mobile cardiac telemetry will also be performed for a week after the end of stimulation and for a week at 3 months after surgery. An Apple watch will be used to detect AF episodes, if any, until the completion of the 3 Month Visit 7-day Mobile Cardiac Telemetry.

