- Surgical implantation- The study design is inspired by spinal cord stimulation, which is a procedure used for pain control. It is standard for spinal cord stimulation to include a trial period that last 4-29 days during which the patient carries an externalized lead connected to a neuromodulator. All devices are removed at the completion of the trial period. The overall infection rate of the trial period was 1.2% (one out of 84 patients). The low infection rate was attributed to strict asepsis, double layer hydrocolloid dressing during the trial, prophylactic antibiotics, operator experience, and patient education. With these techniques, two-stage procedures with extended trials do not seem to increase the incidence of infections for spinal cord stimulation. The PI and several co-investigators are cardiac electrophysiologists with experience in pacemaker/ICD implantations. [name] or [name], experienced neurosurgeons who are familiar with spinal cord stimulator implantations, will serve as a co-investigator. They will train the PI and other co-investigators in performing the procedure using externalized lead. Both of them have agreed to perform the implant procedures. The implantation procedures will be performed in full aseptic conditions. Antibiotics will be administered at the beginning of the procedure. Because this is a subcutaneous implantation, no fluoroscopy is needed. In our initial canine studies, we used Cyberonics wrap VNS electrodes to wrap around a small subcutaneous nerve and delivered electrical current only to that nerve. While effective, that approach requires a large incision to identify the subcutaneous nerves. A large incision is highly undesirable and may increase the complications. Therefore, in most recent NIH-funded canine studies, we have inserted subcutaneous electrodes without specifically identifying subcutaneous nerves. Because the skin is extremely well innervated, we posit that a blindly inserted lead will come in contact of subcutaneous nerves. The results showed that within a week of the stimulation, the average ventricular rate of persistent AF had dropped significantly. Therefore, we will insert electrode lead in the subcutaneous tissues blindly through a Tuohy needle. Figure 1 shows the site of insertion is in the left upper thorax, which is convenient to the patient. In canine studies, multiple other stimulation sites in the thorax had the same antiarrhythmic effects. The exact site of insertion will be determined by patient and/or operator preference. The leads will be secured to the skin by a skin suture similar to that is done with spinal cord stimulation. The remaining lead is externalized and connected to a neurostimulator. Double layer hydrocolloid dressing will be used to cover the externalized lead and the neurostimulator. Lead impedance will be checked at this time because swelling or hematoma could increase the impedance. This surgical procedure will be repeated for the control group crossing over to the experimental group. The second procedure will take place no more than 2 weeks from the Week 3 Visit. If the

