
**Figure 1.** Site for lead insertion. We will insert the lead in the upper thorax 3 cm beneath the clavicle where the skin is innervated by nerves from the stellate ganglion.

second procedure has to take place more than two weeks, the subject will have to undergo a separate pre-op visit which will include a 12-lead EKG, Labs (CBC, BMP), INR if the patient is taking coumadin and pre-op instructions. The procedure will be exactly the same but for the second time, the implant site will be 1-2 cm above or below the original implant site and the stimulation will be turned on. Lead impedance will be checked again once the lead is placed into the chest.

- Randomization-will occur after the implant of the first lead implantation. Randomization will be done electronically within Red Cap.
- Telemetry- The patient will be continuously monitored in the hospital per PI's discretion.. Additional ECG electrodes will be used for telemetry recordings. The ECG signals will be transmitted to the heart station staffed by experienced technicians for heart rhythm monitoring.
- NeuroStimulator programming-program the output to 3.5mA
- SKNA Recording-Skin Nerve Activity recording will be done to compare interactions. The methods of recording are summarized in Figure 2 below.

**Figure 2.** SKNA recording during 6-min walk. The colored dots show electrode location. A shows the ME6000 device. B shows the location of ECG patch electrodes (red buttons) and reference electrode (black button). C shows a second bipolar recording on the right arm. From Supplement Figure 1 of Doytchinova et al.

- A 6-min walk will be conducted to estimate the functional status at baseline (prior to implantation) and during follow up visits (Figure 2). The test will be performed according to the protocol used by Bittner et al. Briefly, we will measure a 30-meter (roughly 100 ft) course in the clinical and recovery area. The patients will be instructed to walk from end to end at their own pace while attempting to cover as much ground as possible in the allotted period of 6 minutes. A research coordinator will time the walk test, called out the time every 2 minutes, and encourage the patient every 30 seconds in a standardized fashion (while facing the patient and using one of the two phrases "You're doing well" or "Keep up the good work"). Patients will be allowed to stop and rest during the test, but are instructed to resume walking as soon as they felt they are able to do so.

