**The following pairs of secondary null and alternative hypotheses will be tested:**

- 1) that the trajectories of reduction of AF burden by time between treatment and control groups are the same versus that the trajectories are different;
- 2) that reduction of AF burden in treatment group does not depend on time versus that the reduction of AF burden is dependent on time;
- 3) that effects of ScNS and sham stimulations on ventricular rate control during AF are the same for the treatment and the control groups versus that the effects are different between the two groups;
- 4) that reduction of SKNA is the same between the treatment and the control groups versus that the reduction of SKNA is different between the two groups;
- 5) that improvement of quality of life is the same between the treatment and the control groups versus that the improvements of QoL is different between the two groups.
- 6) There is a reduction of AF burden after crossing over from control to experimental group

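### The fall in AF burden after crossover is listed as a hypothesis to test, but the plan gives it no test, no reference period and no defined week origin

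*Combined protocol and SAP*

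**What the plan says.** **Status of the question.** Crossover reduction of AF burden is the fifth secondary objective in Sections 1.1 and 3, and the fifth secondary efficacy endpoint in Section 9.1. The endpoint lists in Sections 1.1 and 3 stop at four. Section 9.1 introduces its secondary list as pairs of null and alternative hypotheses for testing. Item 6 is a single directional statement with no null: "There is a reduction of AF burden after crossing over from control to experimental group".

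**Analysis.** Section 9.4.3 says that patients who cross over are "treated the same way as patients on the treatment arm for weeks 1-3". The output is "The averages and SDs of AF burden will be computed for each week from baseline to week 6 for this group", shown graphically. Modelling is optional: "Linear mixed models may be employed to explore the temporal changes in this subset of patients".

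**Timing.** Section 1.2 states: "Second procedure is to be done within two weeks of the Week 3 Visit for crossover patients". Section 8.1 agrees: "The second procedure will take place no more than 2 weeks from the Week 3 Visit". A longer gap is foreseen: if the "second procedure has to take place more than two weeks, the subject will have to undergo a separate pre-op visit". No upper limit is given for that route.

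**Baseline.** The Synopsis says of crossover patients: "They will repeat the baseline visit, procedure visit and all follow-up visits post-procedure". In the Section 1.3 schedule, the procedure-day and week 1 to 3 columns carry the footnote for repetition after crossover. The Baseline column does not.

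**The concern.** A hypothesis that is listed for testing should have a contrast, a reference period and a test fixed in advance. Here all three are open, and so is the time axis. The analyst could choose after seeing the data whether active weeks are set against the original baseline, the sham weeks or some repeated baseline, and whether any model is fitted at all. In a subset of at most 15 patients, those choices could decide whether a reduction is reported.

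The comparator matters most. Section 9.4.2 takes the pre-surgery AF burden from the eligibility recording. Section 5.1 allows that recording to be up to six months old, and Section 5.2 excludes patients with no AF episode during monitoring. Later weeks carry no such condition; Section 9.1 scores a first week without AF as zero. A fall from that baseline can therefore appear with no treatment effect.

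The Synopsis also frames all five secondary objectives as differences between the two randomised groups. A crossover open only to controls cannot supply such a difference for objective 5.

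**Working it through.** **Inputs**
- Sham phase before crossover: 3 weeks (Sections 1.1 and 6.3).
- Stimulation after the second implant: 2 weeks (Section 1.2).
- Telemetry after the second implant: 3 weeks, so two stimulated weeks and one after lead removal (Sections 1.2 and 1.3).
- Delay *g* from the week-3 visit to the second implant: 0 to 2 weeks as the target, longer after a separate pre-op visit (Sections 1.2 and 8.1).
- End of the table: week 6 (Section 9.4.3).

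**Step 1: the plan's own figure.** Numbering treatment weeks consecutively gives 3 + 3 = 6. This reproduces week 6 and holds for any *g*, so on this reading all three post-implant weeks are in the table.

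**Step 2: the calendar reading.** In weeks since the first implant, stimulation runs from 3 + *g* to 5 + *g*, and the post-removal week from 5 + *g* to 6 + *g*. Within week 6:
- stimulated weeks kept = min(2, max(0, 3 − *g*))
- post-removal week kept = max(0, 1 − *g*)

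| Delay *g* (weeks) | Stimulated weeks kept, of 2 | Post-removal week kept, of 1 |
|---|---|---|
| 0 | 2 | 1 |
| 1 | 2 | 0 |
| 2 | 1 | 0 |
| 3 | 0 | 0 |

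Up to a one-week delay no stimulated week is lost. At the two-week limit one of two is lost. Losing both takes three weeks or more, which is beyond the target but not barred.

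**Step 3: alignment.** On the calendar reading, week 6 is the post-removal week for a patient with no delay, the second stimulated week for a delay of one week, and the first for a delay of two. On the treatment-week reading, weeks 3 and 4 look adjacent although an unmonitored gap of varying length lies between them. That would distort the graph, and also any model that enters week as a continuous variable.

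**Step 4: is there another baseline?** Section 1.3 marks telemetry at eligibility, procedure day, week 1, week 2 and three months, and Section 8.1 gives the same list. None is marked in the Baseline column or between the week-3 visit and the second implant. Even a repeated baseline visit would therefore yield no new telemetry AF burden. The Apple Watch is worn in the gap, but as a secondary monitor used to count AF episodes.

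**Step 5: what could be paired.** The procedure-day and week-1 recordings cover weeks 1 and 2 of each implant. Every patient who crosses over should thus have sham weeks 1-2 and active weeks 1-2 from the same telemetry system.

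**Step 6: number of patients.** 30 randomised 1:1 gives at most 15 controls. At the 70% retention in Section 9.2, 15 × 0.7 = 10.5, so about 10 if every retained control crosses over. The documents give no figure for uptake or for delay.

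**The case against.** A reader might infer that the plan drops stimulated weeks from its table. The documents do not support that. Section 9.4.3 never refers to calendar weeks, its preceding sentence points to weeks 1-3 of the treatment arm, and 3 + 3 is exactly 6. The absence of telemetry in the gap favours the same reading, since waiting weeks would have nothing to tabulate. What stands is only that the origin is not stated.

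A reader might also infer that most stimulated weeks could be lost. Even on a calendar count, that does not happen within the two-week target. The week after lead removal should not be counted as stimulated.

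It would also go too far to say that the plan compares crossover burden with a biased baseline, or that no valid comparison is possible. Section 9.4.3 names no comparator. It tabulates sham and active weeks side by side and allows a mixed model. The accurate statement is that no test is pre-specified.

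On the repeated baseline visit, the schema figure is not available here, and its note on activities to be repeated before the second procedure may cover baseline items. Section 1.3 does mark pre-op instructions, CBC and BMP for repetition. The mismatch between the Synopsis and the schedule's column footnotes remains.

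Finally, the crossover was added to help recruitment, follows unblinding of controls (Section 6.3), is optional and runs in one direction. Descriptive reporting is therefore defensible. That argument stands, but the endpoint should then not be listed for testing.

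**Conclusion.** The concern holds in this form: hypothesis 6 is listed for testing, and the plan specifies no contrast, reference period or test for it. This does not depend on how weeks are numbered.

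The undefined week origin is a second, smaller gap. Its cost is nil on the treatment-week reading and conditional on the calendar reading, where 2, 2, 1 and 0 of 2 stimulated weeks are kept for delays of 0, 1, 2 and 3 weeks.

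Regression to the mean would apply to any comparison with the eligibility recording. Its size cannot be derived, because the documents give no week-to-week variability of AF burden within patients. Fifteen patients is a ceiling that assumes every control crosses over. The primary analysis is not touched.

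**What to change.** 1. In Section 9.4.3, number the crossover weeks from the second implant and show the sham and active phases as separate series.
2. Analyse hypothesis 6 as a paired within-patient difference: mean AF burden in active weeks 1-2 minus the same patient's mean in sham weeks 1-2, with a signed-rank test and an interval. State its null in Section 9.1, and say how a patient missing one of the four weekly recordings is handled.
3. Do not use the eligibility recording as the comparator.
4. Label the result open-label and self-selected. Correct the Synopsis stem that frames objective 5 as a between-group difference.
5. If the sponsor prefers not to test, remove item 6 from the hypotheses and call endpoint 5 descriptive.
6. Reconcile the Synopsis with the Section 1.3 schedule on whether the baseline visit is repeated, and align the endpoint lists in Sections 1.1 and 3 with Section 9.1.

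The cost is wording only, because both pairs of weeks are already monitored. Limits remain. All patients cross in one direction, so period effects cannot be separated from treatment. If patients with a bad sham phase are likelier to cross over, some regression to the mean persists even with the sham weeks as reference. At most 15 patients contribute.

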#### **9.4.4 SAFETY ANALYSES**

- **Safety Endpoints**
  - Safety shall be evaluated throughout participation in the study:
  - Freedom of major implant adverse events related to the procedure
  - Infection
  - Lead, extension or migration
  - Persistent pain at the lead site
  - Freedom of Third Degree AV Block at any anatomic level associated with any one of the following conditions
  - Bradycardia with symptoms presumed to be due to AV Block
  - Arrhythmias and other medical conditions that require drugs that result in symptomatic bradycardia
  - Documented periods of asystole > 3.0 seconds or any escape rate <40 beats per minute in awake, symptom-free patients

- Freedom of Second-degree AV block regardless of type or site of block, with associated symptomatic bradycardia
- Freedom of skin irritation related to the ECG patches, Mobile Cardiac Telemetry patch
- Freedom of allergic response to the implanted lead or materials used

The number as well as percent of patients experiencing a safety outcome listed above will be summarized overall and by randomized group in the safety set.

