### 1.3 SCHEDULE OF ACTIVITIES (SOA)

	Eligibility visit	Baseline	Procedure Day (lead implant) and post-operative observation****	1-week visit****	2-week visit****	3-week visit****	3-month visit*****
Screening and eligibility	x						
Obtain Informed consent	x						
Medical history/demographics		x					
Height/Wt/BMI		x					
Hospital Admission			x				
12 Lead EKG		x	x	x	x	x	x
INR (in subjects taking Coumadin)		x	x				
Pre-op instructions		x				x b	
Pregnancy test-Blood or urine for females with childbearing potential			x				
Pre procedure antibiotic			x				
Surgical Implantation			x				
Randomization (after surgery)			x				
Apple Watch Monitoring		x	x	x	x	x	x
Telemetry			x				
NeuroStimulator programming			x				
SKNA recording at rest		x	x	x	x	x	x
SKNA recording during 6-min walk*		x		x	x	x	x
Mental Math Test **		x		x	x	x	x
Discharge/patient teaching***			x				
Removal of Lead					x		

Echocardiogram	x					x	x
Mobile Cardiac Telemetry	X a		x	x	x		x
AFEQT-AF QOL questionnaire		x				x	x
EQ-5D-5L QOL questionnaire		x				x	x
CBC		x				X b	x
BMP		x				X b	x
BNP		x					x
Catecholamine levels		x					x
Subject Stipend	x	x	x	x	x	x	x
Subject Parking fee	x	x	x	x	x	x	x
Assess for Serious Adverse events and Adverse Events	x	x	x	x	x	x	x

The materials and the times of collection for Aim 1A. Labs=laboratory tests; CBC=complete blood count; BMP=basic metabolic panel; BNP=B type natriuretic protein; INR=international normalized ratio. \*if subject is able to complete, \*\*will complete only if unable to complete 6 min walk, \*\*\*discharge day is based on PI decision. \*\*\*\* will only be repeated for control subjects that crossover to experimental group \*\*\*\*\*will only be done on experimental group and control subjects that do not cross over a. Eligibility 7-Day Mobile Cardiac Telemetry is available for potential subjects who may not have had an ePatch monitor completed b. will only be repeated by the crossover group before second procedure

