## 2.3 RISK/BENEFIT ASSESSMENT

### 2.3.1 KNOWN POTENTIAL RISKS

The Immediate risks include the risks associated with surgery such as pain, allergic reaction to the drugs used during surgery, bleeding and death. The possibility of a second surgery increases the previous risks.

The long-range risks include the following:

Because ScNS remodels the stellate ganglion and reduces sympathetic outflow, it is possible to slow down the sinus rate or atrioventricular (AV) conduction. If the following serious side effects are observed, the ScNS will be terminated:

- Third-degree AV block at any anatomic level associated with any one of the following conditions:
  - Bradycardia with symptoms presumed to be due to AV block.
  - Arrhythmias and other medical conditions that require drugs that result in symptomatic bradycardia.
  - Documented periods of asystole  $\geq 3.0$  seconds or any escape rate  $<40$  beats per minute (bpm) in awake, symptom-free patients.
- Second-degree AV block regardless of type or site of block, with associated symptomatic bradycardia

- Infection of the implanted devices
- Persistent pain at the lead site not responsive to drug therapy.
- Allergic response to the implanted lead or materials used
- Lead, extension or migration that results in loss of ability to perform ScNS

The following adverse events will be managed medically

- Skin irritation related to prolonged placement of 7-day Mobile Cardiac Telemetry patch.
- Pain, goosebumps, hot flashes, and other uncomfortable feelings related to electrical stimulation of the subcutaneous nerves.

Alternative methods of treating drug resistant symptomatic AF include catheter ablation procedures and open-heart surgery, both carry significant risks of morbidity and mortality.

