#### Potential risks

- *Redness/Infection:* The overall infection rate is expected to be 1.2%. All infection will be promptly treated with antibiotics and assess if lead removal is necessary. It is expected to the patient will experience skin irritation/edema 3-7 days post procedure. If an infection is mild can be treated with an oral antibiotic and watched closely.
- *Lead extension or migration:* This will be managed by repositioning or removing the lead. The lead cannot be advanced.
- *Persistent pain at the lead site not relieved with OTC medication:* Persistent pain or discomfort will result in lead removal.
- *Allergic reaction:* The patients may be allergic to the local anesthetic agent, the dressing material or the device itself. These allergic reactions will be treated medically and by the device removal.

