#### 6.1.2 DEVICE ENERGY AND ADMINISTRATION

The experimental group will receive stimulation ScNS at 3.5mA output, while the control group will receive no stimulation for 2 weeks.

The control group will have an option to crossover to the experimental group after three weeks from the first procedure and receive stimulation ScNS at 3.5 mA output.

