### 6.3 MEASURES TO MINIMIZE BIAS: RANDOMIZATION AND BLINDING

The patient will be consented to undergo surgery. After the device implantation, the patients will be randomized to experimental and control groups using Redcap. We will attempt to blind the patients, although the tingling or pain associated with the stimulation may make blinding difficult. All data analyses performed by the co-investigators and the rhythm analyses performed by the Mobile Cardiac Telemetry system technicians will be blinded. The experimental group will receive stimulation at 3.5 mA output, while the control group will receive no stimulation. Data will be obtained during this time to determine atrial arrhythmia frequencies in both groups. The device will then be removed at the end of the second week. After the third week, we will give the option to the control group to crossover to the experimental group. This group of patients will undergo a second procedure to receive stimulation at 3.5 mA and we will follow up for another 3 weeks and 3 months post second procedure.

We will tell the patients that they will be randomized into experimental group or control group during surgery. We will attempt to blind the patients, although the tingling or pain associated with the stimulation may make blinding difficult. We will explain to all patients they may or may not feel tingling and/or pain during the 2-week stimulation time but will not tell them which group they are assigned to. All data analyses performed by the co-investigators and the rhythm analyses performed by the 7-day non-invasive monitoring system technicians will be blinded. After 3 weeks post-procedure, we will unblind the control group to give them the option of crossing over to the experimental group to receive the treatment. If they agree, these group of patients will forego the 3-month follow-up visit and will proceed with a second procedure along with follow up visits post-second procedure. Data will be obtained during this time to determine AF burden in all groups.

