### 9.3 POPULATIONS FOR ANALYSES

1. Safety set: the set of patients who have undergone surgery to insert the subcutaneous lead
2. modified intention-to-treat set: the set of patients who have either the subcutaneous nerve stimulation or the sham stimulation performed AND have baseline average AF burden AND at least the first week's post-stimulation average AF burden.

Our sensitivity analysis on the modified intention-to-treat set will be using the safety set: we will assume 0 reduction in AF burden for patients missing either the baseline or the first week post-baseline AF burden.

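### Safety outcomes are tabulated over all of participation by randomized group, so crossover controls' events after a second implant and 3.5 mA stimulation are counted under sham

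*Combined protocol and SAP*

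**What the plan says.** Section 9.4.4 sets the window: "Safety shall be evaluated throughout participation in the study". It then lists the outcomes (among them infection, lead migration, lead-site pain, AV block, patch skin irritation and allergic response) and says that the number and "percent of patients experiencing a safety outcome listed above will be summarized overall and by randomized group in the safety set". No test is planned.

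Section 9.3 defines the population by surgery alone: "Safety set: the set of patients who have undergone surgery to insert the subcutaneous lead". It does not assign patients or events by treatment received.

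Section 6.1.2 provides that "The control group will have an option to crossover to the experimental group after three weeks from the first procedure". Section 6.3 states the exposure that follows: "This group of patients will undergo a second procedure to receive stimulation at 3.5 mA". In the Schedule of Activities (1.3), the columns from procedure day to the 3-week visit, which include the adverse-event row, carry a footnote that they "will only be repeated for control subjects that crossover to experimental group". Section 2.3.1 accepts the added hazard: "The possibility of a second surgery increases the previous risks".

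The only analysis set apart for crossover patients, the last part of 9.4.3, concerns AF burden. No section cuts the safety data at crossover, reports the crossover period on its own, or tabulates safety by treatment received.

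**The concern.** A control who crosses over stays in Group B for a table by randomized group. If that patient has an infection, lead-site pain or AV block after the second implant, the plan as written puts the event in the sham column, although it arose under active treatment. Two distortions follow:

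- **Stimulation-related outcomes.** Events caused by stimulation enter both columns, so the difference between them shrinks.
- **Implant- and patch-related outcomes.** A crossover control has two implants and Group A has one. By the telemetry row of the Schedule of Activities, Group A wears the patch for four 7-day periods (procedure, week 1, week 2, 3 months) and a crossover control for at least six (three, repeated). A percentage of patients ignores this.

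Both distortions make stimulation look safer than it is. This is the only between-group safety summary in the plan. The overall column does not help, because it mixes sham-only and stimulated patients over one denominator.

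**Working it through.** **Inputs from the documents.** Arm size is 15 (section 9.2). It reproduces: (76.3 - 5)/44.8 = 1.59; the normal formula at two-sided 0.025 and 80% power gives 8 per arm; 8/0.864 (minimum Wilcoxon efficiency) rounds up to 10; 10/0.70 rounds up to 15. The only event rate is in section 2.3.3: "The overall infection rate is expected to be 1.2" (percent). Section 8.1 gives its source as one of 84 patients, and 1/84 = 1.2%. No safety figure by group is stated.

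**Assumptions.** Let *p* be the risk per implant, *s* the risk per stimulation course and *c* the share of controls who cross over. The documents give neither *s* nor *c*. Reading 1.2% as a risk per implant is also an assumption. Risks are taken as independent.

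**Formulas (expected share of patients with an event).**
- Group A: A = 1 - (1 - p)(1 - s)
- Controls before crossover: p
- A crossover control over all of participation: X = 1 - (1 - p)²(1 - s)
- Controls as tabulated: B = (1 - c)p + cX
- True difference: A - p = (1 - p)s
- Tabulated difference: A - B = (1 - p)s - c(1 - p)A

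The last term is positive for any c above 0 once there is any risk, so some dilution follows from any uptake. The tabulated sign reverses when c exceeds s/A.

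**Case 1: p = 5%, s = 20% (both assumed).** A = 1 - 0.95 × 0.80 = 24.0%. Controls before crossover: 5.0%. True difference: +19.0 points. X = 1 - 0.9025 × 0.80 = 27.8%.

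| Uptake c | Controls as tabulated | Tabulated difference |
|---|---|---|
| 0% | 5.0% | +19.0 |
| 50% | 16.4% | +7.6 |
| 75% | 22.1% | +1.9 |
| 100% | 27.8% | -3.8 |

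At 50% uptake, (19.0 - 7.6)/19.0 = 60% of the difference is lost. Reversal in expectation needs c above 0.20/0.24 = 0.83.

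**Case 2: p = 1.2%, s = 20%.** A = 1 - 0.988 × 0.80 = 21.0%, and the true difference is 0.988 × 0.20 = +19.8 points. It is tabulated as +9.4 at 50% uptake (about 52% lost) and -0.9 at 100%.

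**Case 3: implant-only outcome, s = 0, p = 1.2%.** The true difference is zero. With full crossover, controls show 1 - 0.988² = 2.4% against 1.2% in Group A. With p = 5% the spurious sham excess is 4.7 to 4.8 points (0.05 × 0.95 = 0.0475).

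**Uptake needed for reversal, s from 5% to 30%.** Above 0.81 to 0.97 at p = 1.2%; above 0.51 to 0.90 at p = 5%; above 0.34 to 0.81 at p = 10%.

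**Chance in a trial of this size.** With 15 per arm, p = 5% and s = 20%, the probability that sham shows more affected patients than Group A is 3% with no crossover, 24% with about half crossing over and 51% with all crossing over.

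**The case against.** A reader might infer that the true safety difference will be hidden or reversed. The documents do not support that. Crossover is optional and no uptake is stated. Section 10.4 says the option was added to help recruitment by assuring everyone access to stimulation, which makes some uptake likely but gives no figure. At zero uptake the planned table is correct, and at the 1.2% implant risk reversal needs more than about four in five controls to cross over. Nor is the infection example a reversed difference: with no stimulation effect the true difference is zero, so what appears is a spurious excess.

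A reader might also infer that the trial's main conclusion or participants' protection is at risk. The primary endpoint in 9.4.2 is measured at week 1, before crossover, and the safety table carries no test or decision rule. Each event is recorded with onset time, severity and relatedness (8.3.3, 8.3.4), serious events go to the monitoring board within 7 to 10 days (10.1.6), and telemetry alerts reach the investigators (8.1, 8.2).

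The infection effect is also small in patients: 15 × 0.012 = 0.18 expected in Group A against 15 × 0.0239 = 0.36 in sham. Even with 45 implants, the chance of no infection at all is 0.988^45, about 58%.

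These points limit the consequence and the severity. They leave the rule itself unanswered: onset times make a split possible, but the plan does not call for one, although it separates crossover patients for AF burden.

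**Conclusion.** The point holds in this form: by its own wording, 9.4.4 counts events under active treatment in crossover controls as sham events. Dilution for stimulation-related outcomes and a spurious sham excess for implant-related outcomes follow in expectation from any uptake above zero. Hiding or reversing a real stimulation risk is possible, but needs high uptake or a per-implant risk that is large relative to the stimulation risk, and the documents establish neither. The percentage-point figures are illustrations that rest on the assumed risks of 5% and 20%, on reading 1.2% as per implant, and on independence. This should be fixed. It concerns how a descriptive table in a 30-patient study will be read, not an error rate or the primary result.

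**What to change.** In section 9.4.4:

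1. Make the between-group safety table cover first implant to the week-3 visit, before any crossover, by randomized group. Controls are unblinded at that point anyway (6.3).
2. Report crossover controls' events from the second implant onward in a separate table, with the numbers of implants and stimulation courses as denominators. Label any pooling with Group A as non-randomized, since these patients chose treatment after unblinding. List onset relative to both implants, because a late event from the first site could otherwise be assigned to the second by date alone.
3. Keep a whole-participation summary by randomized group only if it is labelled as including active treatment in crossover controls. If it is dropped, list the events that fall outside tables 1 and 2 (after week 3 in Group A and in controls who do not cross over, and between week 3 and a second implant).

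The length of safety follow-up after crossover must also be reconciled. The footnote in 1.3 limits the 3-month visit to the experimental group and controls who do not cross over, while 1.2 and 6.3 describe 3-month follow-up after the second procedure.

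The cost is a change of wording and one extra table. Onset time is already collected (8.3.4), so no new patients or procedures are needed. The downside is that the controlled safety comparison covers only about three weeks.
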